#### 4.3.5. Imputation of Incomplete Dates

An incomplete date is any date for which either the day, month or year is unknown, but all three fields are not unknown. An incomplete date occurs when the exact date an event occurred or ended cannot be obtained from a subject. For many of the analyses, a complete date is necessary in order to determine if the event should be included in the analysis (i.e., if the event is treatment-emergent) or to establish the duration of an event. In such cases, incomplete dates will be imputed.

For purposes of imputation, all events with an incomplete end date are assumed to have ended on or before the day the form was completed. To minimize bias, the project statistician will impute dates in a systematic, but reasonable manner. If the month/year is the same as the Day 1 month/year then the date will be set to the date of Day 1. In other cases, missing days will be imputed as the day component of Day 1; missing months/years will be imputed as the month/year of Day 1. For nonexistent dates occurring at the end of a month created by this imputation method, the first date of the next month will be used (e.g. Day 1 = 31JAN2017, incomplete date = XXFEB2017 -> imputed date = 01MAR2017).

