#### Duration of current episode of alopecia

Date of Informed Consent minus the onset date of current episode of Alopecia as reported on the History of Alopecia page of the CRF.

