### **6.3.1. Adverse Events**

Adverse events will be mapped to a preferred term and system organ classification by Medical Dictionary for Regulatory Activities (MedDRA) version 22.0.

An overall summary will be presented which includes the number of TEAEs and the number and percentage of subjects who experienced at least one TEAE. This summary will also include:

- Any TEAE
- Any Serious TEAE
- Any Mild TEAEs
- Any Moderate TEAEs
- Any Severe TEAEs
- Any Related TEAEs
- Any TEAEs leading to discontinuation
- Any Related TEAEs leading to discontinuation

Additional summaries of TEAEs will be provided showing the number and percentage of subjects who experienced at least one TEAE. These summaries will be presented by system organ class (SOC), preferred term (PT) and maximum severity. If a participant reports the same PT multiple times within the same SOC, that PT will only be counted once within that SOC for that participant. As with the PT, if a participant reports multiple conditions within the same SOC, that SOC will only be counted once for that participant. In the summary, SOC will be listed in ascending alphabetical order; PTs will be listed in order of descending frequency for all participants within each SOC.

The occurrence of TEAEs related to study medication will be tabulated by SOC, PT and maximum severity. Serious adverse events (SAE) will be presented by system organ class (SOC), preferred term (PT) and maximum severity. SAE related to study medication will also be presented by SOC and PT.

All AEs reported will be listed by individual subject, showing both verbatim and preferred terms. All AEs reported with a start date prior to the initiation of study medication will be excluded from the TEAE tables but will be included in the listings.

Missing onset dates will be imputed as previously outlined in Section 3.3.5 as required to determine TEAEs.

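### The SAP fills incomplete dates from Day 1 with no bounds, so some adverse events that began inside the treatment-emergent window can be dated after it, and end dates can precede start dates

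*SAP*

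**What the plan says.** SAP 4.3.5 has one rule for any date with some parts known and others not. For the day: "missing days will be imputed as the day component of Day 1". For the month or year: "missing months/years will be imputed as the month/year of Day 1". A partial date in Day 1's own month is moved to Day 1: "If the month/year is the same as the Day 1 month/year then the date will be set to the date of Day 1". If the result is not a real calendar date, "the first date of the next month will be used"; the SAP's example is "Day 1 = 31JAN2017, incomplete date = XXFEB2017 -> imputed date = 01MAR2017". The only bound concerns end dates: "all events with an incomplete end date are assumed to have ended on or before the day the form was completed".

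Section 6.3.1 sends adverse event onsets to this rule: "Missing onset dates will be imputed as previously outlined in Section 3.3.5 as required to determine TEAEs". The SAP has no Section 3.3.5; the rule is in 4.3.5. The treatment-emergent definition in SAP 4.3.6 runs from first dose to 30 days after Visit 9 or last dose.

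SAP 4.3.6 also defines the duration of the current episode as "Date of Informed Consent minus the onset date of current episode of Alopecia", taken from the alopecia history form. Sections 4.3.2 and 6.2.7 split subjects on that duration at 4 years.

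**The concern.** A fill anchored on Day 1 suits an event in the Day 1 month, because it keeps the event treatment-emergent. Later in the study the same fill can move the onset forward, and nothing stops it passing the end of the window or the subject's last contact. An event that did begin in the window would then drop out of every treatment-emergent table.

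Two further effects follow from using one rule for all dates. An end date can be placed before its own start date. And if the rule reaches the alopecia onset date, some subjects could fall on the wrong side of the 4-year cut, a factor that feeds 18 planned tables (two in each of the nine sets 14.2.15 to 14.2.23).

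**Working it through.** **Inputs.** The rule from SAP 4.3.5; the window and duration definitions from SAP 4.3.6; Visit 9 at Day 169 and screening up to 30 days before Day 1 from the schedule of assessments; a planned study period of June 2018 to July 2019 from the protocol synopsis. Assumptions: Day 1 falls between 01JUN2018 and 15JAN2019 (229 dates), the window ends 30 days after the last dose, and every possible onset date counts equally. The percentages are therefore shares of possible dates, not forecasts of events.

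**Check against the SAP.** Day 1 31JAN2017 with XXFEB2017 gives 31FEB2017, which does not exist, so 01MAR2017. This matches the SAP's example.

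**1. Onset with only the day missing.** With last dose on Day 169 the window ends on Day 169 + 30 = 199. Example: Day 1 30AUG2018, Day 169 is 14FEB2019, window ends 16MAR2019. XXMAR2019 becomes 30MAR2019, which is outside, although any onset from 1 to 16 March was inside.

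Over all Day 1 dates and all onsets from Day 1 to last dose + 30 days:

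| Last dose | Possible onset dates | Pushed past the window | Share |
|---|---|---|---|
| Day 169 | 229 × 199 = 45,571 | 942 | 2.1% |
| Day 85 | 229 × 115 = 26,335 | 1,933 | 7.3% |
| Day 29 | 229 × 59 = 13,511 | 2,807 | 20.8% |

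With last dose on Day 169, 112 of the 229 Day 1 dates have at least one affected onset. All losses are in the 30-day tail. The fill moves a date by at most 30 days (from the 1st to the 31st, or to the 1st of the next month), so an onset on or before the last dose stays within last dose + 30. The tail holds 229 × 30 = 6,870 dates; within it the shares lost are 942/6,870 = 13.7%, 1,933/6,870 = 28.1% and 2,807/6,870 = 40.9%.

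**2. Onset with day and month missing, year after Day 1, fields filled separately.** The result is the Day 1 anniversary, Day 1 + 365 days = Day 366, against a limit of Day 199. All 19,701 of 19,701 such dates fall out, on-treatment ones included. Example: Day 1 15NOV2018, onset 2019 becomes 15NOV2019; the window ends 01JUN2019.

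**3. End dates.** Day 1 05SEP2018, start 20OCT2018, end XXOCT2018 becomes 05OCT2018, before the start. For a complete start and a day-missing end in the same month, 253,589 of 715,061 combinations (35%) are impossible. For a year-only end in the Day 1 year, which becomes Day 1, 25,641 of 25,870 (99%) are.

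**4. Episode duration, if the rule applies.** Example: Day 1 15SEP2018, consent 27AUG2018, onset 2014 becomes 15SEP2014; the duration is 1,442 days / 365.25 = 3.95 years. Every year-only onset in the Day 1 year minus 4 is classed under 4 years when consent precedes Day 1 in the same calendar year. Averaged over the assumed Day 1 dates, 66% of the possible true dates in that year are at least 4 years (consent 1 day before Day 1), or 59% (30 days before). The share depends on the consent date: 151/365 = 41% for 1 June and 243/365 = 67% for 1 September. Year-only onsets 5 to 12 calendar years back all go to 4 years or more, and those 0 to 3 years back all go to under 4, which is right for at least 99.6% of possible dates. A year-only onset in the Day 1 year becomes Day 1 and gives a negative duration when consent is earlier (27AUG2018 minus 15SEP2018 = −19 days).

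**The case against.** The strongest reply is that this is rare and small. Protocol 8.3.4 has the investigator ask at each visit about changes since the previous one, and visits are two to four weeks apart. An onset with an unknown month should be uncommon. That stands: a reader might infer that the rule strips on-treatment events from the safety tables generally, and it does not. With only the day missing, no on-treatment onset is lost.

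A reader might also infer that year-only episode onsets as a class are sorted into the under-4-year group. The documents do not support that. Filling field by field confines the error essentially to one calendar year. The broad claim would need month and year to be treated as one unit that overrides a recorded year. The wording does not rule this out, but then every year-only adverse event in step 2 would be dated Day 1 and kept, so the two strong claims cannot both hold. With consent on Day 1, or screening that crosses New Year, the four-year error also disappears or changes. Consent before Day 1 is nevertheless the expected case, since Protocol 8.1.4 and 8.1.5 require the screening ECG interpretation and laboratory results to be reviewed before Baseline. The duration definition does not cite 4.3.5, so its use there is not certain.

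The treatment-emergent definition could be read as open-ended after the last dose, which would remove steps 1 and 2. That reading is strained: the 30-day limit most naturally governs both anchors.

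On end dates, no planned table reports event duration and listings show partial dates as recorded, so the impossible dates change no identified result. That also stands.

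**Conclusion.** The point holds as a minor defect in a stated rule, not just missing detail: followed literally, the rule gives wrong dates. Its main effect is on treatment-emergent status: 2.1% of possible onset dates with the day missing for a subject who completes treatment, rising to 20.8% for one who stops at Day 29, all in the post-treatment tail. On-treatment losses need a missing month, a year after the Day 1 year and field-by-field filling. The episode-duration error is confined essentially to year-only onsets four calendar years before the Day 1 year, with consent before Day 1 in the same calendar year, and arises only if the rule is used for history dates.

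These sizes rest on the assumed range of Day 1 dates, equal weight for each onset date, and a window closing 30 days after last dose. The documents do not give the number of partial dates, so the effect on the actual tables cannot be sized. The primary SALT analysis in all subjects is unaffected.

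**What to change.** Replace the imputation paragraph in SAP 4.3.5 with separate rules:

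- **Adverse event onset:** the earliest date consistent with the known parts but not before Day 1, unless the known parts or the end date show that onset preceded Day 1. For an event that began on or after Day 1, the imputed date cannot be later than the true one, so no event that began in the window is pushed past its end. In the examples, XXMAR2019 becomes 01MAR2019 and 2019 becomes 01JAN2019 (Day 48 for Day 1 15NOV2018); both are inside.
- **End dates:** the latest date consistent with the known parts, not before onset and not after the form date.
- **Alopecia history:** state that the Day 1 fill does not apply. Any mid-period date used instead should be described as approximate at the 4-year cut. A single date such as 1 July still puts every onset from that year on one side, so it is not clearly more accurate there.
- **Cross-reference:** change the citation in 6.3.1 to Section 4.3.5.

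The cost is one paragraph and one reference, with no new data. The downside is small: a few events of uncertain timing will be counted as treatment-emergent, which is the cautious direction for safety tables.

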#### 4.3.6. Definitions and Terminology

##### Day 1

Day 1 is defined as the date of the initial study medication dose as reported on the study medication usage page of the CRF.

##### Study Day

Study Day is defined relative to Day 1. Thus, the study day of an event is calculated as:

Study Day = ((event date – date of Day 1) + 1) for dates on or after Day 1

Study Day = (event date – date of Day 1) for dates prior to Day 1

##### Study Day

Study day will be relative to the defined Day 1.

##### Study Visit

Study Visit is the nominal visit as recorded on the CRF.

##### Days on Study

Days on Study is calculated as: study discontinuation date - informed consent date + 1

#### Last Dose of Study Medication

Last Dose of Study Medication is defined as the last date that the subject took oral medication in the treatment period as determined by last date of recorded on the study medication usage page of the CRF.

#### Study Medication Exposure (days)

Study drug exposure is defined as the (date of last dose – date of first dose + 1).

#### Dose Interruptions

Dose interruption is defined as 2 or more consecutive days where ‘None’ was checked for the number of doses per day field on the study medication page of eCRF.

#### Missed Dose

A missed dose is defined as a single day where ‘None’ was checked for the number of doses per day field on the study medication page of eCRF.

#### Study medication compliance (%) based on number of doses

The compliance with the dosing regimen will be calculated based on the subject-specific dose regimen as, [(study medication exposure days - number of days with less than the subject-specific expected number of doses) / (study medication exposure days)] x 100.

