## APPENDIX 15. STUDY MEDICATION INSTRUCTION SHEET

### General Instructions:

1. Each month during the treatment phase of the study, the site staff will provide you with a one-month supply of study medication (with a few extra doses in case of spillage, loss or a missed appointment).
2. Do not take the study medication on an empty stomach. Food improves how much drug is absorbed and how much drug reaches your blood, which will give the drug the best chance of reaching your scalp.
3. You will drink one bottle of study medication two times a day with a meal (approximately 8 to 12 hours between doses).
4. Make sure the cap is tightly secured and gently shake the study medication before taking a dose.
5. Swallow all the study medication in the bottle.
6. Add water to the study medication bottle and drink the liquid, followed by a large glass of water.
7. Do not change your dose without talking to the study doctor.
8. Avoid excessive natural or artificial ultraviolet radiation (e.g., sunlight, tanning beds) and use sunscreen, if excessive sun exposure cannot be avoided.
9. Remember to bring your compliance sheet, study medication bottles, both used and unused, to each study visit.

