### **5.3. PER PROTOCOL (PP) POPULATION**

The Per-Protocol (PP) population is defined as all subjects who are randomized and do not have any major protocol violations. Major protocol violations that will lead to exclusion from the PP are defined as:

1. Inclusion or Exclusion criteria not met
2. Concomitant medications taken during the study that interfere with efficacy
3. Did not administer at least 75% of study medication
4. Did not complete Week 24 (Visit 9).

This population will be used for supportive analyses of key efficacy endpoints.

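### SAP 4.3.6 compliance counts fully dosed days rather than doses, and the 75% per-protocol criterion has no stated calculation

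*SAP*

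**What the plan says.** SAP 4.3.6 defines one compliance percentage, under the heading "Study medication compliance (%) based on number of doses". It starts from exposure days, subtracts the "number of days with less than the subject-specific expected number of doses", and divides by exposure days. Exposure is "date of last dose – date of first dose + 1", so the window closes at the last dose actually taken, not at Week 24.

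Two neighbouring definitions in SAP 4.3.6 draw on the same daily record. "A missed dose is defined as a single day where" None is ticked "for the number of doses per day field on the study medication page of eCRF". "Dose interruption is defined as 2 or more consecutive days where" None is ticked.

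SAP 5.3 and Protocol 9.2 both list, as the third major violation that removes a subject from the PP population, "Did not administer at least 75% of study medication". Neither says how the percentage is obtained. The fourth violation is not completing Week 24.

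The regimen is two single-dose bottles a day; Protocol Appendix 15 tells the subject: "You will drink one bottle of study medication two times a day with a meal". Protocol 3.4 allows the frequency to be changed to once a day after consultation with the Medical Monitor. SAP 6.1 plans summaries of missed doses, dose reductions and compliance (Table 14.1.10).

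**The concern.** The heading promises a count of doses and the formula counts days. With two doses a day the two agree only when every short day is a day with no dose at all. A subject who often forgets one of the two daily doses is scored as if both had been missed.

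This matters mainly because of the PP population. Criterion 3 is worded as an amount of drug and comes with no calculation, and the SAP offers only one compliance percentage to a programmer who has to apply it. PP membership drives the sensitivity analysis of the primary endpoint named in Protocol 9.4.2, which SAP 6.2.3 runs with both LOCF and observed data. With 95 subjects over four arms, about 24 per arm, a few misclassified subjects could move that analysis. Leaving the rule open also lets membership be settled late.

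The missed-dose definition is a separate reporting fault. A day with one of two doses is neither a missed dose nor an interruption, so the missed-dose summary cannot show the commonest form of partial non-adherence.

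**Working it through.** The 75% is a threshold, so there is no stated result to reproduce. The check compares the SAP formula with a dose count.

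**Inputs.** 24 weeks of treatment (SAP 1.1) = 24 × 7 = 168 days. Two doses a day (Protocol Appendix 15) = 336 planned doses. PP threshold 75% (SAP 5.3, Protocol 9.2), which is 0.75 × 336 = 252 doses.

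**Notation.** Over E exposure days, let F be days with both doses, H days with one and N days with none.

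- SAP formula: (E − H − N) / E = F / E.
- Share of doses taken in the window: (2F + H) / (2E) = F / E + H / (2E).

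The dose share exceeds the SAP figure by H / (2E). For a fixed twice-daily regimen within the exposure window, a SAP value of at least 75% therefore guarantees at least 75% of doses. The error there can only exclude.

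**Twice daily for 168 days.**

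| Pattern | SAP formula | Doses taken |
|---|---|---|
| 42 days with none | 126/168 = 75.0% | 252/336 = 75.0% |
| 42 one-dose days | 126/168 = 75.0% | 294/336 = 87.5% |
| 43 one-dose days | 125/168 = 74.4% | 293/336 = 87.2% |
| 84 one-dose days | 84/168 = 50.0% | 252/336 = 75.0% |
| One dose every day | 0/168 = 0% | 168/336 = 50.0% |

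The first two rows give the same SAP value for different amounts of drug. From 43 to 84 one-dose days the subject meets the wording of criterion 3 and falls below 75% on the formula.

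**How often, under an assumption.** Suppose each dose is taken independently with probability p; the documents give no p. A day is fully dosed with probability p², so the expected SAP value is p².

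| p | Expected SAP value | Chance SAP value ≥ 75% | Chance doses ≥ 252 |
|---|---|---|---|
| 0.75 | 56.3% | about 0% | 52.9% |
| 0.80 | 64.0% | 0.2% | 98.9% |
| 0.85 | 72.3% | about 24% | about 100% |
| 0.90 | 81.0% | 97.9% | about 100% |
| 0.95 | 90.3% | about 100% | about 100% |

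**Against planned drug.** A subject takes every dose and has the last one on day 57. Exposure is 57 days, so the SAP value is 57/57 = 100%. Doses taken are 114, and 114/336 = 33.9%.

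**Change to once daily from day 29, all doses taken.** Doses are 28 × 2 + 140 = 196, and 196/336 = 58.3% of planned. If the expected number falls to one, the SAP value is 100%. If it stays at two, it is 28/168 = 16.7%. The SAP does not say which applies.

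**Missed doses.** One dose missed on every day for 24 weeks is 168 doses missed. The SAP definition counts 0, because no day is marked None.

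**The case against.** The strongest reply is that nothing in the SAP says this formula implements criterion 3. Protocol 5.6 also relies on the subject's record and on inspection of bottles, the SAP lists drug accountability separately from drug administration, and Protocol 10.3 has evaluability determined before lock. Criterion 3 could be applied from a bottle or dose count. That stands. A reader might infer that PP membership is already wrong; the documents support only that the criterion has no calculation and that the one compliance percentage defined does not fit its wording.

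A reader might also infer that the formula misclassifies in both directions for any subject. It does not: with fixed twice-daily dosing inside the exposure window it can only exclude. Wrong passes arise only against planned doses. The early-stopping route also needs a subject who stops drug yet counts as having completed Week 24, since one who leaves the study fails the fourth criterion anyway.

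Scoring an authorised once-daily schedule as compliant is a defensible choice. The SAP says it measures adherence to the regimen set for that subject, and SAP 6.1 reports dose reductions separately. The gap is that the handling is not spelled out for criterion 3.

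It is tempting to read the missed-dose definition as a cause of the compliance problem. It does not enter the formula. A subject who misses one dose daily would also show 0% compliance in the same reporting, so the non-adherence would not be hidden altogether.

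Finally, misclassification on a fixed regimen needs at least 43 one-dose days in 168, and the documents do not indicate how common that would be.

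**Conclusion.** The point holds. The formula gives the percentage of fully dosed days between first and last dose, contrary to its heading, and criterion 3 has no stated calculation.

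Conditional on the formula being used for criterion 3, twice-daily subjects with 43 to 84 one-dose days out of 168 would be wrongly excluded from PP. Also conditionally, a subject who stops drug early but attends Week 24 could be wrongly kept, on 33.9% of planned doses in the day-57 example. The counts assume 168 exposure days (except in that example) and a fixed two doses a day; the pass rates further assume independent doses at an assumed p.

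The missed-dose definition is a separate fault, and it holds without any condition.

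The reach is limited to the supportive PP analyses and the compliance and missed-dose table. The ITT primary analysis, the observed-data ITT analysis and the power statement do not depend on it. It should be corrected before unblinding, because PP membership ought not to turn on a rule chosen afterwards.

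**What to change.** Amend SAP 4.3.6 and 5.3 as follows.

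1. Define compliance as 100 × (doses recorded as taken) / (doses expected).
2. State that this figure implements PP criterion 3, with the doses planned over the 24-week treatment period (336 on the twice-daily schedule) as the PP denominator. Using 2 × exposure days instead would repair the one-dose-day problem but would still score 100% for the subject whose last dose was on day 57.
3. State in advance how frequency changes authorised under Protocol 3.4 count in the expected doses, and how partial first and last dosing days count. Keep reporting dose reductions separately.
4. Define missed doses as expected minus taken, and keep interruptions as their own summary.

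The cost is SAP wording and one derived variable with its table. The eCRF already records doses per day, so no new data are needed.
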